8.9.2 Serious Adverse Events (SAE)

An SAE is an adverse event that could lead to any of the following:

CIP Number 2023-A00150-45 Final version 0.2

a) Death

- b) Serious deterioration in the health of the patient, users, or other persons as defined by one or more of the following:
 - 1) a life-threatening illness or injury
 - 2) a permanent impairment of a body structure or a body function including chronic diseases
 - 3) in-patient hospitalisation or prolonged hospitalisation
 - 4) medical or surgical intervention to prevent life-threatening illness or injury, or permanent impairment to a body structure or a body function.

c) Foetal distress, foetal death, a congenital abnormality, or birth defect including physical or mental impairment.

Serious Adverse Events will be collected and reported as described in the Study Procedure Manual.

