Idiopathic PD is characterised by a continuous progression of clinical symptoms and can be preceded by a prodromal phase lasting years or even decades, defined by a specific set of non-motor symptoms such as Rapid Eve Movement (REM) sleep behaviour disorder, depression, constipation, and anxiety. At their onset, motor symptoms are usually unilateral, an asymmetry usually persists through the course of the disease. Bradykinesia, rigidity, and tremor are the typical motor abnormalities of early-stage PD, leading the patient to seek medical attention and guiding the first diagnosis. As the disease progresses, more debilitating symptoms emerge, as motor fluctuations (on/off phases) and dyskinesias manifest (Poewe et al., 2017). Slow walking is a common manifestation of PD that negatively affects patients' performance in daily living activities (Mehrholz et al., 2016; Muslimović et al., 2008). Among the most burdensome characteristics of late-stage PD are instability of posture and gait abnormalities, oftentimes causing falls that can be quite harmful, frequently leading to hospitalisation and reduction in life expectancy ((Verghese et al., 2009, Fasano et al., 2017). Some studies reported that approximately 35% to 90% of PD patients fall at least once a year, with an average rate of 60.5% (Fasano et al., 2017; Pickering et al., 2007; Wood et al., 2002). In another work, it was estimated that roughly 39% of patients sustain multiple falls and fall-related injuries over one year (Allen et al., 2013). Given the high rate of falls during walking in people with PD and the significant burden they impose on quality of life as well as on the health care system, identifying individuals at higher risk and developing rehabilitation programs to reduce such risk is crucial. Motor symptoms are also supplemented by a set of non-motor manifestations which can greatly affect the quality of life of the patients, such as pain, cognitive impairment, apathy and autonomic dysfunction (Chaudhuri and Schapira, 2009).

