8.9 Safety Assessments

Adverse events of special interest, serious adverse events and all device related non-serious and serious adverse events will be collected from the signature of the ICF until the participation of the patient is completed within the study. Serious Adverse Device Effects will be reported to the authorities.

In case an adverse event is suspected during the regular follow-up calls between the patient and the APA specialist, the APA specialist will contact the Investigator to enquire the investigation of the event and the assessment of severity and causality.

Detailed instructions on recording and reporting of serious safety incidents will be provided in the Study Procedure Manual.

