8.9.3 AEs of Special Interest

Given the objective of the study and the disease assessed, AEs of special interest will be collected irrespective of seriousness and relatedness. These AEs are typically ones concerning the motor functions of the patients and include but are not limited to falls, freezing of gait, rigidity, bradykinesia, dyskinesia, dizziness, stiffness, vertigo and in general the worsening of the disease.

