8.9.5 Serious Adverse Device Effect (SADE)

A serious adverse device effect is an adverse device effect that has resulted in any of the consequences characteristic of a serious adverse event (8.7.2). If a serious safety incident occurs related to a device or study procedure, the incident will be recorded in the eCRF and reported to the Ethics Committee as required. Instructions on recording and reporting of serious safety incidents will be provided in the Study Procedure Manual.

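### The protocol defines an SAE by what could happen and a SADE by what did happen, so a device-related SAE need not be a SADE

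*Protocol*

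**What the plan says.** Section 8.9.2 opens with "An SAE is an adverse event that could lead to any of the following". It then lists death, serious deterioration in health and foetal harm. One form of serious deterioration is "in-patient hospitalisation or prolonged hospitalisation".

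Section 8.9.5 says that a SADE is "an adverse device effect that has resulted in any of the consequences characteristic of a serious adverse event". It points to section 8.7.2 for those consequences. No such section exists, because 8.7 is the falls diary and has no subsections. Section 8.9.2 is evidently meant.

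Three other places depend on the definitions:
- Section 8.9 states that "Serious Adverse Device Effects will be reported to the authorities".
- Section 9.2.7 tabulates device-related AEs and SAEs and sends all safety data to listings.
- Section 8.9.3 collects AEs of special interest whether or not they are serious or related: "These AEs are typically ones concerning the motor functions of the patients and include but are not limited to falls, freezing of gait" and others.

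The falls diary (Appendix G) grades each fall from A (serious injury with an emergency visit or admission) to D (no physical injury).

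**The concern.** Seriousness should mean one thing within a protocol. Here, one section asks what an event might have caused and the other asks what it did cause, over the same list. Where the answers differ, the device-related SAE table and the SADE reports would count different events for the same device.

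The gap covers a hazard that the sponsor itself foresees. Section 4.6 describes a display fault in the application that leads to over-large movements and a loss of balance. When such an event ends without injury, the two definitions can part.

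The potential test also has no stated limit. Section 8.9.6 defines intensity, causality and outcome but gives no rule for seriousness. When the APA specialist passes on a suspected event, section 8.9 asks the investigator for severity and causality only. Six sites would each decide what 'could' covers. No Data Monitoring Committee is planned (section 10.1), so the written definitions carry more of the weight.

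**Working it through.** No arithmetic applies. The check is to pass the same events through each definition.

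The potential test in 8.9.2 can be read in two ways. It may concern the type of event (falls as a class can lead to hospital admission), or the particular event once its outcome is known. The protocol does not say which.

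| Event | ADE (8.9.4) | SAE (8.9.2), by type of event | SAE (8.9.2), by this event with known outcome | SADE (8.9.5) |
|---|---|---|---|---|
| Device-related loss of balance, no injury | yes | yes | no | no |
| Device-related fall with hospital admission | yes | yes | yes | yes |
| No-injury fall, not device-related | no | yes | no | no |

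1. **Row 1.** On the by-type reading the event is an ADE and an SAE but not a SADE. It would count among device-related SAEs under 9.2.7 and fall outside the category that 8.9 sends to the authorities. On the by-event reading it is neither an SAE nor a SADE, and the definitions agree.
2. **Row 2.** An event with an actual listed outcome is serious on every reading. The conflict is limited to events with potential but no actual serious outcome.
3. **Row 3.** Whether a grade D fall is an SAE depends entirely on the reading that a site adopts. Under 9.2.7 such a fall would appear in listings and not in the device-related tables.
4. **Which reading was intended?** Collecting falls irrespective of seriousness, separating serious from non-serious device-related events in 8.9, and having a no-injury diary grade all presuppose that some falls are not serious. The by-type reading works against that intent, yet the wording of 8.9.2 permits it.
5. **Data capture.** Falls are collected as AEs of special interest and in the diary, and 8.9 collects all device-related events, serious or not. For these events the conflict changes the label and the reporting route, not whether the event is recorded.
6. **Endpoints.** The safety endpoint in Table 5.1 counts device- and procedure-related adverse events without a split by seriousness, so it is unaffected. The rate-of-falls endpoint comes from the diary and is also unaffected.

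**The case against.** The best defence is that this is a loose phrase with little practical effect. A sensible investigator would judge the particular event, and on that reading the definitions agree. An over-inclusive SAE definition errs on the cautious side. Sections 8.9, 8.9.2 and 8.9.5 leave recording and reporting detail to a Study Procedure Manual that is not shown and may contain working rules. Section 8.9.5 adds a further route, through the Ethics Committee, for serious incidents tied to the device or to a study procedure. Section 12.3 commits the study to MDR 2017/745 and ISO 14155. Section 4.6 reports no device-related adverse events among roughly 2530 insole users, so affected events may be few.

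Much of this stands, and it limits the size of the point. It does not remove it. The definitions are fixed in the protocol, and a manual that narrowed 8.9.2 would contradict it. The Ethics Committee route uses a third term for a serious incident that is not defined, so it does not settle which threshold applies. The insole record says little about the loss-of-balance hazard, which section 4.6 attributes to the application.

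It is also fair to say that the protocol never states which threshold was intended. The preference for the actual-outcome test rests on section 8.9.3 and the diary grades, not on an explicit statement.

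**Conclusion.** The two definitions conflict as written. Read literally, a device-related event with potential but no actual serious outcome is an SAE for the tables and not a SADE for reporting to the authorities, and sites may class no-injury falls differently. The consequence is limited to safety classification and reporting. It cannot be sized from the documents, which give no rate of device-related events of this kind. The conclusion assumes that the reference in 8.9.5 to section 8.7.2 means 8.9.2.

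Four stronger readings are tempting, and the documents do not support them:
- **Every harmless fall is an SAE.** This follows only on the by-type reading, against the evidence of intent above. The remark in section 4.1.1 that falls often lead to hospital concerns late-stage disease, whereas eligible patients are at Hoehn and Yahr stage 2 to 3 and walk unaided for at least six minutes.
- **A count of fall-SAEs can be derived.** Section 4.1.1 says that "approximately 35% to 90% of PD patients fall at least once a year, with an average rate of 60.5" percent. Scaling this to the study would estimate patients who fall, not SAEs.
- **Only SADEs reach the authorities.** Section 8.9 says that SADEs will be reported. It does not say that nothing else will be.
- **The SAE tables would mostly measure falls.** Unless otherwise stated, section 9.2.7 restricts tables and figures to device-related data.

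**What to change.** Put sections 8.9.2 and 8.9.5 on one seriousness threshold. The simplest edit is to give 8.9.2 the actual-outcome test of 8.9.5, so that an SAE is an event that has led to a listed consequence. Correct the cross-reference in 8.9.5 to 8.9.2 at the same time. If the sponsor wants to keep potential-harm events visible, add a separate eCRF flag and tabulate flagged events apart from SAEs.

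The cost is one phrase, one section number and, if wanted, one eCRF field. The sample size, visits and efficacy analyses do not change. The downside is that potential-harm events can then be identified as such only through the flag. For an event that is neither device-related nor of special interest, being an SAE is what brings it into collection under section 8.9, so without the flag a potential-only event of that kind would no longer be recorded.

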8.9.3 AEs of Special Interest

Given the objective of the study and the disease assessed, AEs of special interest will be collected irrespective of seriousness and relatedness. These AEs are typically ones concerning the motor functions of the patients and include but are not limited to falls, freezing of gait, rigidity, bradykinesia, dyskinesia, dizziness, stiffness, vertigo and in general the worsening of the disease.

8.9.4 Adverse Device Effect (ADE)

An ADE is an adverse event related to the use of an investigational medical device. This definition includes adverse events resulting from; insufficient or inadequate instructions for use, deployment, implantation, installation, or operation, or any malfunction of the investigational medical device. It also covers any event resulting from use error or from intentional misuse of the investigational medical device.

8.9.5 Serious Adverse Device Effect (SADE)

A serious adverse device effect is an adverse device effect that has resulted in any of the consequences characteristic of a serious adverse event (8.7.2). If a serious safety incident occurs related to a device or study procedure, the incident will be recorded in the eCRF and reported to the Ethics Committee as required. Instructions on recording and reporting of serious safety incidents will be provided in the Study Procedure Manual.

8.9.6 Assessment Definitions

Assessment of Intensity

The investigator must assess the intensity of the safety event using the following definitions:

- Mild the event causes minimal discomfort and does not interfere in a significant manner with the patient's normal activities.
- Moderate the event is sufficiently uncomfortable to produce some impairment of the patient's normal activities.
- Severe the event is incapacitating, preventing the patient from participating in the patient's normal activities.

Assessment of Causal Relationship

The investigator must assess the causal relationship between the adverse event and the Investigational Medicinal Product (IMP) using the following definitions:

- Probable – the event has a strong temporal relationship to the IMP or recurs on rechallenge, and another aetiology is unlikely or significantly less likely.

- Possible the event has a suggestive temporal relationship to the IMP, and an alternative aetiology is equally or less likely.
- Not related the event has no temporal relationship to the IMP or is due to an underlying/concurrent disorder or effect of another drug (that is, there is no causal relationship between the IMP and the adverse event).

An event is considered causally related to the use of the IMP when the causality assessment is probable or possible.

Assessment of Outcome

The investigator must assess the outcome of an event using the following definitions:

- Recovered the patient has recovered completely, and no symptoms remain.
- Recovering the patient's condition is improving, but symptoms remain.
- Recovered with sequelae the patient has recovered, but some symptoms remain (for example, the patient had a stroke and is functioning normally, but has some motor impairment).
- Not recovered the patient's condition has not improved, and the symptoms are unchanged
- Death

9 STATISTICAL METHODS AND CONSIDERATIONS

The SAP will provide full details of the analyses, data displays, and algorithms to be used for data derivations. It will be written before the first patient is enrolled in the study. All statistical analyses will be conducted by a blinded independent statistician.

9.1 Analysis sets

The Screened set includes all subjects for whom informed consent to participate in the study was obtained and have a subject identification number.

The Full Analysis Set (FAS) includes all subjects randomised to one of the pre-defined treatment arms and who had a baseline gait measurement.

No Per Protocol Set (PPS) is planned to be defined for this study.

The Safety Set (SAF) includes all subjects who were randomised, removing only patients who do not start their assigned therapy.

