	During their routinely scheduled visit at the investigational site patients who express interest in participating in the study will be introduced to the device. If judged to be comfortable with and interested in the technology, patients will return to their home to consider their participation. There is a reflexion period that lasts at least fifteen days up to one month If the patient decides to participate in the study, they return to the site for the screening visit. Once the informed consent is signed the screening assessments will be performed by the investigator (the neurologist). If eligible, the patients will be randomised either into the conventional physiotherapy (CPt control group) or the FeetMe rehabilitation program (experimental group).
	Primary Intervention Period
	Once randomised patients will proceed to the Baseline Visit (BL). At the BL visit, all participants (experimental and CPt control group) will be trained to use the FeetMe devices and will wear the insoles as much as possible throughout the visit. Standard gait and balance assessments will be performed (6 minute walk test (6MWT), MiniBESTest). Additionally, patients will perform multiple clinical assessments designed to assess: disease severity, gait, balance, mobility, etc. by completing different surveys.
	Following the BL visit, all patients will enter an initial 12 week period according to their patient group. Every patient in the study will be provided with a pair of insoles and will take the device to their homes. All patients, whatever the group of randomisation, will be asked to wear them as much as possible for 14 days after the BL visit to allow continuous gait data collection. This will permit the gathering of extensive data on a considerable number of gait parameters in a more familiar and natural setting reflecting real-life conditions. The FeetMe

patients will then continue to use the insoles according to the FeetMe rehabilitation program schedule.						
During the Primary Intervention Period (PIP), all patients will participate in two remote visits: Visit 1 (four weeks after BL) and Visit 2 (eight weeks after BL). During these visits, all patients will perform a short battery of self-reported questionnaires.						

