7.3 Baseline Visit

All randomised patients will participate in the Baseline Visit. This visit will be on the same day as the Screening Visit.

Patients will be instructed in the use of the FeetMe Monitor and wear the insoles for the duration of the visit, while performing a series of assessments.

The following assessments will be performed at the Baseline Visit:

CIP Number 2023-A00150-45 Final version 0.2

- Demographic data collection (month and year of birth; gender, weight, height, leg length, shoe size)
- Recording of relevant medical history, prior medications
- Gait Assessments, which must be performed in ON-phase:
 - 6 Minutes Walk Tests (6MWT)
 - Mini-BESTest

During the 6MWT and the Mini-BEST gait data will be recorded using the FeetMe Rehabilitation or Evaluation application. Specific instructions set out in the Site User Manual must be followed when setting up and executing the assessments.

- Disease specific rating scales:
 - The Movement Disorder Society sponsored Revision of the Unified Parkinson's Disease Rating Scale (MDS-UPDRS)
- Other Assessments:
 - Freezing of Gait Questionnaire (FOG-Q)
 - Parkinson Disease Sleep Scale 2 (PDSS2)
 - Pain VAS
 - Parkinson Disease Questionnaire (PDQ39)
 - Patient Global Impression of Severity (PGI-S)
 - Clinical Global Impression of Severity (CGI-S)

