9.1.1 Usage of the analysis sets

The efficacy analysis will be performed on the FAS. The safety analysis will be performed on the SAF.

Table 9.1 outlines the randomised treatment groups and the analysis sets, for each of efficacy and safety.

Table 9.1 Combination of patient cohorts, patient treatment groups and analysis sets

Randomised treatment group	Efficacy	Safety
Patient group A (conventional physiotherapy)	FAS	SAF
Patient group B (FeetMe Rehabilitation)	FAS	SAF

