9.2.1 Estimands for primary and key secondary objectives

The main treatment policy estimands for the primary and key secondary objectives of this study, are defined in Table 9.2 below. This table describes the four attributes of target population, endpoint, strategy for addressing intercurrent events, and population-level summary for the endpoints (ICH E9 (R1)).

Target population	Endpoint	Strategy for addressing intercurrent events	Population-level summary				
Primary object	Primary objective in line with H0_1_Primary						
Idiopathic Parkinson'sChange baselinefrom to 		All available data to be included. This is in alignment with the FAS definition. If a patient has a fall up to week 12 and has available week 12 gait data, then the week 12 data will be used and the fall ignored. If the week 12 measurement is not available, whatever the reason (death or injury) the baseline data are used (the patient is not excluded).	In Idiopathic PD patients on CPt, what is the change in gait velocity 12 weeks after randomisation, assessed during the 6MWT, between Conventional Physiotherapy and FeetMe Rehabilitation and whilst the patient is on treatment?				
Key secondary	objective in line w	ith H0_2_KeySecondary					
Idiopathic Parkinson's Disease (PD) patients on Conventional Physiotherapy (CPt)	Change from baseline to Week 12 in stance time variability (ms) assessed during the 6MWT.	All available data to be included. This is in alignment with the FAS definition. If a patient has a fall up to week 12 and has available week 12 gait data, then the week 12 data will be used and the fall ignored. If the week 12 measurement is not available, whatever the reason (death or injury) the baseline data are used (the patient is not excluded).	In Idiopathic PD patients on CPt what is the change in stance time variability 12 weeks after randomisation, assessed during the 6MWT, between Conventional Physiotherapy and FeetMe Rehabilitation and whilst the patient is on treatment?				

Table 9.2 Treatment policy estimands for the primary and key secondary objectives

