9.5.1 Analysis for the primary endpoint

The primary outcome (the change in the gait velocity between baseline and week 12, assessed during the 6 Minutes Walk-Test) will be estimated and compared between Feetme rehabilitation and conventional physiotherapy groups using the constrained longitudinal data analysis (cLDA) model proposed by Liang and Zeger including centre as random effect and adjusted for the covariable "already in a rehabilitation program" considered as stratification factor in the randomisation. We chose to use cLDA model in view of its potential advantages compared to the conventional ANCOVA model. First, the cLDA model provides more flexibility in handling missing data by including all observed data, which, in general, results in more power when testing treatment differences compared with the longitudinal ANCOVA model. Second, compared with the ANCOVA model, the cLDA model provides more appropriate confidence interval estimates, especially in the context of randomised clinical trials where proper randomisation ensures baseline balance. In the cLDA model, both the baseline and postbaseline values are modelled as dependent variables using a linear mixed model (using an unstructured covariance pattern model), and the true baseline means are constrained to be the same for the 2 treatment groups. The between-group mean differences in 12-week change in gait velocity will be estimated by the time-by-arm interaction as treatment effect size. The assumptions of the cLDA model will be checked. We will use the analysis of cDLA model residuals by examining graphically the normality of residuals (histogram and Quantile-quantile plot) and by using the Shapiro Wilk test. In case of strong departure from the normality assumptions (even after applying a logarithmic transformation), nonparametric analysis will be used as recommended by Vickers et al. (reference: 1) Andrew J Vickers. Parametric versus non-parametric statistics in the analysis of randomised trials with non-normally distributed data. BMC Medical Research Methodology 2005, 5:35 2) Conover WJ, Iman RL: Analysis of covariance using the rank transformation. Biometrics 1982, 38:715-724.); absolute changes between baseline and 12-week will be calculated and compared between the 2 treatments groups using nonparametric analysis of covariance adjusted for baseline values. The effect size will be assessed by Hedges's g (standardized differences) computed on rank transformed data with its 95% confidence interval (using the method based on noncentral Student distribution which is a corrected version of Cohen's d taking into account the sample size). A sensitivity analysis will be performed excluding from the FAS population patients who have a change in levodopa medication during the first 3 months. For this sensitivity analysis, we will use the same methodology as that described for the primary analysis.

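### The only efficacy set requires a baseline gait measurement taken after open-label randomisation, which the primary model and the falls and scale analyses do not need

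*Protocol*

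**What the plan says.** - **Analysis set.** Protocol section 9.1: "The Full Analysis Set (FAS) includes all subjects randomised to one of the pre-defined treatment arms and who had a baseline gait measurement". The same section adds "No Per Protocol Set (PPS) is planned to be defined for this study", and section 9.1.1 states "The efficacy analysis will be performed on the FAS". The one sensitivity analysis of the primary endpoint (sections 9.2.3 and 9.5.1) removes further patients from the FAS, namely those whose levodopa changed.
- **Order of events.** Randomisation belongs to screening (Table 6.1, section 7.2.1.2). The baseline gait tests come afterwards. Section 7.3: "All randomised patients will participate in the Baseline Visit. This visit will be on the same day as the Screening Visit". The design is open label (section 6.1).
- **Primary model.** Section 9.5.1 fits a cLDA in which baseline and post-baseline values are both dependent variables and the baseline mean is constrained to be equal in the two arms. One reason given is that "the cLDA model provides more flexibility in handling missing data by including all observed data".
- **Other endpoints.** Section 9.5.2 applies the same model to the Mini-BESTest, MDS-UPDRS Part III and PDQ-39. Falls are analysed by a negative binomial model with a log follow-up offset, and no gait term is stated.
- **Estimand.** Table 9.2 is headed as treatment policy and says: "All available data to be included. This is in alignment with the FAS definition". Section 9.2.5 carries that handling over to the other secondary endpoints.

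**The concern.** Entry to the set depends on something that happens after allocation, at a time when the arm can already be known. A patient who misses the baseline gait test but remains in the study may have a valid Week 12 walk, a falls diary and complete questionnaires. Under section 9.1 none of these enters any efficacy analysis, because no other efficacy set exists.

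Three things are at stake. Usable data are lost. No efficacy analysis covers everyone randomised. And a set that is meant to serve a treatment-policy question is narrower than that question calls for.

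**Working it through.** **1. Does each analysis need a baseline gait value?**

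| Analysis | Baseline gait value needed? | Source |
|---|---|---|
| Primary and gait secondary endpoints, cLDA | No: baseline is an outcome with a shared mean, so any one observed value contributes | 9.5.1, 9.5.2 |
| Falls, negative binomial | No: only the count, arm and follow-up time are stated | 9.5.2 |
| PDQ-39, MDS-UPDRS III, Mini-BESTest, cLDA | No: each is modelled on its own values | 9.5.2 |
| Baseline used when Week 12 is missing | Yes, for gait endpoints | Table 9.2 |
| Rank ANCOVA fallback on changes, adjusted for baseline | Yes, for gait endpoints | 9.5.1 |

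The condition serves only the last two rows, but it is applied to all five.

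**2. The plan's own sample size.** Inputs from section 9.4: difference 14 cm/s, SD of change 27 cm/s, correlation 0.5, two-sided 5%, power 80%, dropout 20%.
- SD of change: 27 × √(2 × (1 − 0.5)) = 27 cm/s, as stated.
- The two-sided t test needs 59.4, so 60 per group, with power 80.4% at 60.
- 60 / 0.8 = 75 per group, 150 in total.

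The stated 60, 75 and 150 are reproduced. The 20% allowance is described for the Week 12 measurement only, so a missing baseline would come on top of it.

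**3. Size of the exclusion.** The protocol gives no rate of missing baseline gait measurements, so the share m is an assumption. Evaluable patients per group = 75 × (1 − m) × 0.8, and power comes from the same t test.

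| m (assumed) | Patients of 150 | Evaluable per group | Power |
|---|---|---|---|
| 0% | 0 | 60.0 | 80.4% |
| 2% | 3 | 58.8 | 79.6% |
| 5% | 7.5 | 57.0 | 78.4% |
| 10% | 15 | 54.0 | 76.1% |

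**4. How much of that the cLDA could recover.** Relative to a complete patient, a patient with only a Week 12 value carries 1 − ρ² of the information on the Week 12 mean. At ρ = 0.5 this is 1 − 0.25 = 0.75. At m = 5%, 7.5 × 0.8 = 6 excluded patients would have a Week 12 value, worth 6 × 0.75 = 4.5 complete patients across both arms. The table counts each excluded patient as a complete case, so its power loss is an upper bound on what could be regained.

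**5. What a one-sided exclusion could do.** If a share m of one arm is excluded and differs from the rest of that arm by D in mean outcome, the arm mean moves by m × D. With D = 14 cm/s, that is 0.02 × 14 = 0.28, 0.05 × 14 = 0.7 and 0.10 × 14 = 1.4 cm/s. This illustrates scale only. The documents do not show that such a difference will occur.

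**The case against.** **The event should be rare.** This stands. Baseline follows screening on the same day (section 7.3, Table 6.1), the test is supervised in clinic (section 4.6), sites hold back-up insoles and a device with the Evaluation application (sections 4.7 and 6.4.3), and eligibility requires walking six minutes unaided. A patient who leaves for good on that day would probably supply no later data, so the real loss is confined to patients who miss the test and continue.

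**The term is not defined as an insole recording.** This also stands. A reader might infer that any failed insole or application recording removes a patient from everything, including the Mini-BESTest. Section 9.1 does not say so. Sections 7.3 and 8.1 list the Mini-BESTest among the gait assessments, and in the 6MWT the investigator also measures the distance walked (section 8.1.1). On a broad reading, a completed walk or Mini-BESTest may satisfy the condition.

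**Bias by arm.** A reader might infer that the exclusion biases the comparison. Both arms do the same test before any assigned therapy begins, and no mechanism for a difference is documented. Known allocation makes a difference possible and no more.

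**Contradiction with Table 9.2.** A reader might call the FAS a plain contradiction of the all-data statement. The table itself ties that statement to the FAS, so the two are in tension but do not contradict each other in plain text. Nor is the advantage of the cLDA forfeited: the missingness planned for is at Week 12, and patients with only a baseline value stay in the model.

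**Some procedures do need a baseline.** True of the two shown in the working. They justify their own data requirement. They do not justify excluding a patient from falls, PDQ-39 or MDS-UPDRS III, or from the primary cLDA.

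**Conclusion.** The point holds in limited form. The protocol fixes one efficacy set by a measurement taken after open-label randomisation. That measurement is not needed for the primary cLDA or for the falls and scale analyses. Patients who miss it and remain in the trial lose all their efficacy data, which sits badly with a treatment-policy aim.

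The size cannot be taken from the documents and is probably small. With an assumed 2-5% missing it is 3 to 8 of 150 patients and at most about 0.8 to 2.0 percentage points of power (80.4 − 79.6 and 80.4 − 78.4). This rests on the planning values in section 9.4 and on 20% Week 12 dropout applied on top. For falls and the non-gait scales, the excluded patients' data are lost entirely. The documents establish neither a bias between arms nor a direct contradiction in the text.

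The change is still worth making: the rule is stated outright, it discards usable data for no analytical gain in most analyses, and it is easily removed.

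**What to change.** 1. In section 9.1, define the FAS as all randomised patients, analysed as randomised, and delete the clause that requires a baseline gait measurement.
2. In sections 9.5.1 and 9.5.2, state that each cLDA uses every FAS patient with a baseline or Week 12 value for that endpoint, and that the falls model uses every FAS patient with any falls follow-up.
3. State that the rule in Table 9.2 for a missing Week 12 value and the rank ANCOVA fallback in section 9.5.1 apply only to patients with a baseline value for the endpoint concerned.
4. Amend the reference to the FAS in Table 9.2 to match.
5. If wanted, keep the present set as a sensitivity set, and then define which measurement qualifies.

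The cost is a few sentences in sections 9.1, 9.2.1 and 9.5. No extra data or patients are needed, and the sample size stays at 75 per group, 150 in total.
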